- Cumulative radiation exposure in the preceding 12 months totalling 10mSv or more.

*The lifetime risk for a healthy adult of developing a fatal malignancy following exposure to ionising radiation similar to that expected in our study is approximately 1:1800. This is low compared with the average UK cancer mortality rate of about 1 in 4, leading to a marginal added risk due to the study participation. However, higher BAT activation is expected in young adults⁴. We have therefore decided to enrol young adults in our study, in order to be able to demonstrate the principle of glucagon induced BAT activation in a small pilot study. Thus, while the risk e risk remains very small but is slightly greater in younger subjects. Given that only those subjects who have demonstrated significant rises in EE in response to glucagon would be put forward for PET-CT scanning, we expect to be able to achieve the aims of our study with a minimal number of subjects exposed to additional ionising radiation.

Study Visitsfor Objective 1

After the screening visit, volunteers will be invited to attend 7 study visits. There will be a time interval of at least two days between visits.

During Visit 1, 2 and 3, volunteers will receive an intravenous infusion of (A) saline under thermoneutral conditions, (B) saline with cold stimulationor(C) glucagon, allocated in a randomised single-blinded fashion. Resting and stimulated energy expenditure will be measured with a standard indirect calorimeter (as previously used successfully in this laboratory³). Supraclavicular deposits of BAT will be imaged using infrared thermography (i.e. thermal imaging).

If the volunteers have demonstrated a measurable rise in EE or BAT activation during these first 3 study visits, they will be asked to complete Visits4to 7. During Visit 4 and Visit 5, volunteers will receive an intravenous infusion of (A) saline or(B) glucagon, allocated in a randomised single-blinded fashion, and undergo a 60-minute dynamic FDG PET-CT scan.During Visit 6 and Visit 7, volunteers will receive an intravenous infusion of (A) saline (with cold stimulation) or (B) glucagon, allocated in a randomised single-blinded fashion, and undergo a 60-minute MRI scan.

Details of Study Visit Preparation, Blood Sampling, GlucagonInfusion, and Cold Stimulation.

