After the acclimatisation period and acquisition of control images, study images will be acquired continuously for 10 minutes prior to the start of the infusion. End-infusion study images will be acquired continuously during the last 10 minutes of the infusion. The visit protocol for Visits 1, 2 and 3 is outlined in Figure 1.

From each thermal image stream, using existing methodology², the maximal temperature over defined regions of interest in the neck region will be recorded. Data will be analysed using Prism.

Figure 1 – Visit Protocol for Study Visits 1, 2 and 3 for Healthy Volunteers

Details of PET-CT

Volunteers who have demonstrated rises in EE or BAT activation in response to glucagon infusion over Visits 1-3 will be invited to attend Visits 4 and 5, to measure BAT activation using PET-CT at the Imanova Imaging Unit in Hammersmith Hospital. The study timetable for Objective 1 is shown in Figure 2.

Positron emission tomography (PET), has become a routine research tool over the past 25 years. We will use 18-fluorodeoxyglucose (¹⁸F-FDG), an analogue of glucose to measure the metabolic rate of BAT. Metabolically active brown adipocytes avidly take up glucose, and are expected to increase their metabolic rate, and therefore the uptake of both glucose and 18F-FDG following stimulation with cold or glucagon. ¹⁸F-FDG has been previously used to study BAT activation with PET⁶⁻⁸. Dynamic PET data will be collected from the upper torso and neck will be acquired, areas known to contain significant amounts of BAT. In order to quantify the PET data adequately, a low-dose CT scan of the upper torso and chest will be conducted prior to each PET scan, in order to estimate tissue attenuation of the PET signal. The ionizing radiation exposure from the two¹⁸F-FDG PET scans (maximal administration of 185MBq per scan) and two low-dose CT scans of the upper torso, is expected to be approximately 9.5mSv.

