At each PET-CT visit two intravenous cannulae will be inserted into the forearm or cubital veins in order to administer the ¹⁸F-FDG and glucagon or saline infusion (via one cannula), and collect blood samples during the course of the PET-CT scans (via the second cannula). The glucagon or saline infusion will be initiated and then the volunteers will be then be led into the scanner room where the 18F-FDG bolus will be administered immediately prior to the scan. Subjects will undergo a brief low dose CT followed by a 60-minute dynamic PET scan. Volunteers will be lying on a bed throughout the scan and can communicate with (and will be reassured by) the radiographer and researchers as necessary.

[figure not shown]
Images will be quantified by deriving standard outcome parameters for the defined regions of interest, using established methodology. All of the PET-CT scans will also be formally reported by a consultant radiologist. Although the PET-CT scans are not performed with the aim of clinical diagnosis, and this may not be considered of diagnostic quality, they may reveal an incidental finding relevant to the subjects health status. In this situation the report would be communicated to the volunteer and the volunteer's GP, who would arrange the appropriate specialist referral. A significant abnormality would exclude that volunteer from further participation in the study.

Figure 2 – Study Timetable for Objective 1

OBJECTIVE 1: To assess BAT activation in response to glucagon infusion in healthy volunteers using PET-CT and thermal imaging.

N=16 healthy male volunteers to complete this arm

- NB. - Visits 1-3 will be allocated in a random order.
 - Visits 4 to 7 will only be undertaken if there has been a demonstrable response to glucagon infusion over Visits 1-3.
 - All infusions will be single-blinded.

Details of MRI

Volunteers who have successfully completed visits 1-5 will also be invited to attend Visits 6 and 7. The objective of these visits is to measure BAT activation using MRI at the Imanova Imaging Unit, Hammersmith Hospital.

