Subjects will be given a personal study code number which will be used throughout the study and in the analysis of data. Coded samples or images will also be treated with confidentiality when undergoing analysis. Analysis will take place in the Imanova Clinical Imaging Centre and the Department of Investigative Medicine at Hammersmith Hospital and be carried out by the researchers themselves. The data will be kept in a secure environment in these departments, under the authority of [name]. Data will be stored for 15 years after completion of the study. Only the researchers will have access to this data.

REGULATORY COMPLIANCE

The Chief Investigator has obtained approval from the xxx Research Ethics Committee. The study has been submitted for Site Specific Assessment (SSA) at each participating NHS Trust. The Chief Investigator will obtain a copy of the Trust R&D approval letter before accepting participants into the study. The study will be conducted in accordance with the recommendations for physicians involved in research on human subjects adopted by the 18th World Medical Assembly, Helsinki 1964 and later revisions.

Consent to enter the study will be sought from each participant only after a full explanation has been given, an information leaflet offered and time allowed for consideration. Signed participant consent will be obtained. The right of the participant to refuse to participate without giving reasons will be respected. After the participant has entered the study the clinician remains free to give alternative treatment to that specified in the protocol at any stage if he/she feels it is in the participant's best interest, but the reasons for doing so should be recorded. In these cases the participants remain within

the study for the purposes of follow-up and data analysis. All participants are free to withdraw at any time from the protocol treatment without giving reasons and without prejudicing further treatment.

The study may be subject to inspection and audit by Imperial College London under their remit as sponsor and other regulatory bodies to ensure adherence to GCP and the NHS Research Governance Framework for Health and Social Care (2nd edition).

FUNDING AND INDEMNITY

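### Nothing in the available text keeps the thermal, PET or MRI image readings masked to condition, because who is blinded is not stated and the only code identifies the volunteer

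*Protocol*

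**What the plan says.** **Blinding.** In the protocol's Study Visits for Objective 1, the infusions at Visits 1–3, 4–5 and 6–7 are "allocated in a randomised single-blinded fashion". The notes to Figure 2 add: "All infusions will be single-blinded". Neither place says which party is blinded.

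**Who analyses.** Data Handling places the analysis at the imaging centre and the investigators' department, and says it will "be carried out by the researchers themselves".

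**Coding.** The same section says: "Subjects will be given a personal study code number which will be used throughout the study and in the analysis of data". Of the images it says: "Coded samples or images will also be treated with confidentiality when undergoing analysis". Confidentiality is the only purpose given.

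**Readings.** For thermal imaging, "the maximal temperature over defined regions of interest in the neck region will be recorded", taken from ten-minute streams before and at the end of the infusion. For PET-CT: "Images will be quantified by deriving standard outcome parameters for the defined regions of interest". Details of MRI describes separating brown from white fat at rest and then measuring temperature change. It mentions no regions of interest. None of these sections says who makes the readings or whether that person knows the condition. The SAP's Statistical Analysis section does not mention masked reading either; I make no claim about other SAP text.

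**What rests on the readings.** The first outcome measure is the change in brown adipose tissue (BAT) signal on all three modalities. Study Visits for Objective 1 also lets a volunteer proceed to Visits 4–7 on a rise in either energy expenditure (EE) or BAT activation, with no threshold given.

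**The concern.** Placing a region on an image involves some judgement, and the protocol states the result it expects: Details of PET-CT anticipates that tracer uptake will rise with cold or glucagon. A reader who knows the condition can lean towards that result without meaning to. Each volunteer is his own control, so a lean that follows the condition goes straight into the within-person difference.

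Two things are at stake. One is the saline-versus-glucagon contrast on imaging, which is the substance of Objective 1. The other is the gate: a thermal reading can help decide who goes on to two PET-CT scans, with an expected exposure of about 9.5 mSv. A volunteer who enters on EE does so on a calorimeter measurement, which has no region to place.

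**Working it through.** **1. What the code can hide.** Each volunteer has one code for up to seven visits. It takes the same value at the saline, cold and glucagon visits, so it carries no masking of condition. Masking would need a code that differs by visit and has no visible link to date or order.

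**2. Where discretion remains.** A maximum within a drawn region is computed, so the reader has no say in that step. The reader's influence lies in where the region is placed and, for the thermal streams, which frames are used. Anatomy does not settle the boundary on PET-CT: the protocol's Background says that CT cannot tell brown fat from white, and that brown fat shows up on PET-CT only when stimulated.

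**3. Why random order does not help.** Write a reading as

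reading = true signal + visit effect + b × (1 if glucagon, 0 if saline),

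where b is the shift caused by knowing the condition. The expected paired difference, glucagon minus saline, is δ + b, with δ the true effect. Randomised order balances the visit effect. It leaves b untouched.

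**4. The plan's own figure.** The SAP states 95% power with 4 per group for PET/CT. It gives no effect size or SD, so this cannot be reproduced. Solving backwards at two-sided 5%, it implies a standardised difference of about 2.83 (paired t) or 3.09 (two-sample t). The present point neither disputes that figure nor depends on it.

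**5. Illustration of size.** The documents give no value for b. I *assume* no true effect (δ = 0), normal differences, and a constant shift b in units of the SD of the paired difference. For a two-sided 5% paired t-test,

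P(reject) = P(|T| > t₀.₉₇₅,ₙ₋₁), with T noncentral t on n − 1 df and noncentrality b√n.

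The sample sizes are 4 (the SAP's PET/CT figure, treated here as 4 pairs) and 16 (the protocol's number to complete Objective 1).

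| n | critical t | b (SD) | b√n | P(reject) |
|---|---|---|---|---|
| 4 | 3.182 | 0 | 0 | 5% |
| 4 | 3.182 | 0.25 | 0.5 | 6.5% |
| 4 | 3.182 | 0.5 | 1.0 | 11.1% |
| 16 | 2.131 | 0 | 0 | 5% |
| 16 | 2.131 | 0.25 | 1.0 | 15.5% |
| 16 | 2.131 | 0.5 | 2.0 | 46.5% |

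The noncentrality grows with √n, so a larger sample makes a fixed reading bias more likely to be declared significant. The SAP names repeated-measures ANOVA with Tukey's test, not a paired t-test, so the table shows direction and rough order only.

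**The case against.** The strongest reply is that silence is being read as fact. A reader might infer that only the volunteer is blinded, that the same individuals infuse, read the images and decide who proceeds, and that every reading is therefore made with the condition known. The documents do not support that. Single-blinded is never defined, the researchers are a group working at two sites, and no division of tasks is given. The sentence on who analyses sits in a section about confidentiality, not in an image-reading plan. This part of the reply stands, and it limits the point to what the text fails to prevent. Staff who apply cooling must know that condition, but that does not show that they also read the images.

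Discretion may also be small: the thermal and PET methods are described as existing or established, and the camera is calibrated against a temperature-controlled block. That narrows the scope for bias. It does not say who places the regions or with what knowledge.

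The direction of bias is not clear for every contrast. The SAP's stated question is cold versus glucagon, and the protocol expects a rise with both, so expectation could act on both sides and partly cancel. I therefore confine the directional claim to saline versus glucagon.

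The consultant radiologist's reports on the PET-CT and MRI scans might look like a safeguard. The accompanying text concerns incidental findings, not BAT quantification.

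Lastly, the protocol presents this as a pilot. That bears on the scale of the remedy, and the remedy here is small.

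**Conclusion.** The point holds as a gap in the safeguards: the available text provides no masking of the person who reads the thermal and PET images, or any MRI measure of BAT. A condition-linked bias in saline versus glucagon is possible, and the thermal route through the gate to Visits 4–7 shares the exposure. The EE route is less exposed.

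Its size is unknown. A reader might take the 46.5% as this trial's error rate; it is not. It comes from an assumed 0.5 SD shift at n=16, in a test the SAP does not name. At the SAP's PET/CT sample size of 4, the same assumptions give 6.5–11%. Nor do the documents show that any reading was in fact biased.

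The change is worth making because the readings carry the main outcome and the protection is cheap.

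**What to change.** 1. **State who is blinded** in the protocol, for the infusions and separately for image reading.
2. **Recode the files.** An existing team member who does not read that image set holds the key and renames the thermal, PET and MRI files to random codes, with visit, date and condition removed.
3. **Read in random order under a fixed anatomical region rule**, covering which thermal frames are used. Use CT only to locate the anatomical region, since it does not separate brown from white fat. For MRI, set the region on the resting images.
4. **Lock the values before the condition is attached.**
5. **Handle the gate volunteer by volunteer.** Read and lock each volunteer's Visit 1–3 thermal set under masked codes before the Visit 4 decision. Locking everything only at the end of the study would come too late for this. Read the images for the final analysis masked as well.
6. **State the limit.** Cold may not be maskable where the vest or its effect is visible; saline versus glucagon can be. The protocol's PET visits compare saline with glucagon without cold, so they can be masked. The MRI visits compare cold with glucagon and may be only partly maskable.

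The SAP is written in the past tense, so readings may already exist. If the images are among the data kept for 15 years, a masked re-read is still possible.

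The cost is a little more file handling and key-keeping within the existing team, with the key-holder kept off the reading of that set. Sample size, visits and infusions do not change.

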**NCT No. NCT01935791**

## Statistical Analysis

Based on previous studies of the hormonal and cold exposure effects on human BAT activity 1, 2, we calculated that, for an equivalent rise in EE, a sample size of 4 per group (glucagon versus control) would have 95% power to detect a significant difference between the effects of cold exposure and glucagon using F-FDG PET/CT in confirmed BAT-positive volunteers. Because of safety considerations, as PET/CT scans expose healthy patients in this study to ionising radiation, we limited this study to males only and to the smallest possible sample size to answer our initial question about the differential effects of cold exposure and glucagon administration on human BAT activity for a given rise in EE.

All data were analysed using GraphPad Prism 6 software (GraphPad Software, Inc., San Diego, CA, USA). Results are presented as means ± standard error of the mean. One-way repeated measures anova with Tukey's test was used to compare differences between the three intervention groups. A p value < 0.05 was considered to indicate statistical significance.

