Intravenous infusions by the Section of Investigative Medicine follow protocols established after extensive experience investigating the physiological role of numerous peptide hormones in humans. Single and combination infusion of gut hormones have been performed on large cohorts of human volunteers within this department without adverse event (ethics refs: 2002/6261 and 09/H0707/76).

This healthy human volunteer investigation will comply in full with the standard procedures that were developed at the behest of the RPMS ethics committee. This followed extensive discussion with a number of experts and their purpose is to ensure safety and efficacy in peptide preparation and administration. The procedures used in this study will be the same as those used in previous studies carried out by our group (ethics refs: 2002/6261 and 09/H0707/76).

Indirect calorimetry is a well-established technique in our laboratory. The calorimeter captures expired air from a large, transparent canopy, worn over the head and thorax, and is typically very well tolerated. Thermal imaging remotely measures the emission of infrared radiation from the surface of the skin using a small camera, does not involve ionizing radiation, and therefore does not expose the subjects to any additional risks.

¹⁸F-FDG PET-CT imaging is a well-established methodology and the Manov group has conducted a number of similar studies over the last 6 years. While PET studies involve additional ionizing radiation exposure for the participants, the levels of exposure from this study are in line with other experimental protocols conducted in healthy volunteers. We are proposing a T2* (echo planar) MR scanning protocol in a 3T scanner to perform fat extraction and MRI thermography. Magnetic resonance imaging is safe and widely used in clinical practice. It does not involve ionizing radiation.

METHOD FOR OBJECTIVE 1

To assess BAT activation in response to glucagon infusion in healthy volunteers using PET-CT, thermal imaging and MRI.

We have chosen one gut hormone, glucagon, to investigate using both thermal imaging, PET-CT and MRI. We have previously shown that glucagon induces a large rise in energy expenditure (EE) in healthy volunteers without any side effects³. To minimise radiation exposure, only volunteers who have a demonstrable rise in energy expenditure (EE) in response to glucagon infusion will undergo PET-CT scans.

Recruitment

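### The SAP's 95% power is for cold versus glucagon on PET/CT, but the protocol schedules PET only under saline and glucagon

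*SAP*

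**What the plan says.** **SAP, Statistical Analysis.** The sample-size sentence gives "a sample size of 4 per group (glucagon versus control" and says that this "would have 95% power to detect a significant difference between the effects of cold exposure and glucagon", measured by "PET/CT in confirmed BAT-positive volunteers". The next sentence says the study was kept as small as possible, because of radiation, "to answer our initial question about the differential effects of cold exposure and glucagon administration on human BAT activity". No effect size, SD, sidedness, or choice between paired and unpaired comparison is stated. The only test named is a one-way repeated-measures ANOVA with Tukey's procedure, which "was used to compare differences between the three intervention groups".

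**Protocol version 3, Study Visits for Objective 1.** "During Visit 4 and Visit 5, volunteers will receive an intravenous infusion of (A) saline or(B) glucagon", with a dynamic FDG PET-CT scan at each. Cold is named as a condition for Visits 1 to 3 (calorimetry and thermal imaging) and for one of the two MRI visits, but not for the PET visits. Details of PET-CT repeats that the infusion at a PET visit is glucagon or saline, and has it started before the tracer is given.

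**Protocol, numbers.** Recruitment (Objective 1) asks for 20 volunteers with 16 completing. Safety and Wellbeing of the Volunteers allows up to 16 to have PET-CT, at most two scans each, with total exposure not above 9.5 mSv.

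**Protocol, Outcome Measures.** The first outcome is the change in BAT signal from baseline to the glucagon-stimulated state, by PET-CT among other methods.

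**The concern.** A power statement holds for one contrast, in one population, with one design. Here the contrast is cold against glucagon on PET, and the protocol's PET visits contain no cold condition. If the protocol was followed, the question that the SAP calls its initial one has no PET data, and the comparison that PET can make (glucagon against saline, the PET form of the first outcome) has no stated power.

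The figure also supports the SAP's argument that the smallest adequate number of healthy volunteers was exposed to radiation. If it belongs to a different comparison, that argument has no stated numerical basis for the scans the protocol describes. Each document is definite when read alone. Read together, they do not settle which PET comparison was intended, in how many volunteers, or how it was to be tested.

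**Working it through.** **1. Conditions by visit, from Study Visits for Objective 1**

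| Visits | Measurement | Conditions |
|---|---|---|
| 1–3 | Energy expenditure, thermal imaging | saline; saline with cold; glucagon |
| 4–5 | PET-CT | saline; glucagon |
| 6–7 | MRI | saline with cold; glucagon |

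There are 2 PET conditions and 0 cold PET scans, and the cap is 2 scans per volunteer.

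**2. Can two scans serve both questions?** The first outcome needs saline and glucagon. The SAP question needs cold and glucagon. Together they need three conditions. Because the infusion begins before the tracer bolus, a scan gives one value under one condition and no PET baseline of its own. Three conditions do not fit in two scans.

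**3. Does the named test fit?** A three-condition ANOVA matches Visits 1–3. PET has two conditions, so no test is named that matches it.

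**4. Reproducing the 95%.** This is not possible: the mean difference, SD, within-person correlation and sidedness are all absent. One can only solve for the effect that 4 per group would need at alpha 0.05, two-sided.

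- Paired t: power = P(T′ > t₀.₉₇₅,ₙ₋₁), where T′ is noncentral t with n − 1 df and noncentrality δ√n, and δ is the mean difference in SDs of the paired differences. At n = 4 (df 3), 95% needs δ = 2.83 (noncentrality 2.827 × 2 = 5.65).
- Two independent groups of 4 (df 6, noncentrality d√(4/2)): d = 3.09.
- Two groups, normal approximation: (1.960 + 1.645) × √(2/4) = 2.55.

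So 95% is attainable at 4 per group if the true difference is very large. The documents give nothing against which to judge whether it is.

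**5. The same formula at the two sample sizes.** At n = 16 (df 15), 95% needs δ = 0.97 (noncentrality 0.965 × 4 = 3.86). Over an assumed range of δ:

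| Assumed δ | Power, n = 4 | Power, n = 16 |
|---|---|---|
| 0.5 | 11% | 46% |
| 1.0 | 29% | 96% |
| 1.5 | 53% | >99% |
| 2.0 | about 75% | >99% |
| 3.0 | 97% | >99% |

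A simulation of 400,000 runs gave 0.290 (n = 4) and 0.962 (n = 16) at δ = 1.0.

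**The case against.** - **Control may mean saline.** The SAP labels its groups glucagon versus control. If control is saline, the label matches Visits 4 and 5. The ambiguity is real, since the protocol also calls cold a positive control. But on the saline reading the SAP sentence contradicts itself, because the difference it claims to detect, and the question it then restates, are both cold against glucagon. Either reading needs a correction.
- **Cold appears in Details of PET-CT.** It does, as an expectation about tracer uptake after cold or glucagon. It allocates no scan. Figure 2 is not shown; if it listed a cold PET visit, it would conflict with the visit text.
- **4 and 16 can coexist**, one as a minimum for a PET subset and the other as completers or a ceiling. They are not an arithmetical contradiction, and more volunteers raise power for a given effect. However, the protocol derives its number partly from the BAT PET literature, while the SAP says it used as few as possible, and neither document connects the two.
- **The power table does not measure the fault.** This is correct. The fault is a missing condition. The table shows only how far any statement depends on inputs that are not given, and it should not be read as showing that 95% is implausible.
- **The SAP text may describe a later design.** It is undated and in the past tense, so this is possible, but neither document says so. It bears on which text to correct, not on whether they disagree.

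**Conclusion.** The concern holds and must be fixed. The only power figure in the documents is for cold versus glucagon on PET/CT, and protocol version 3 allocates PET to saline and glucagon alone. As written, the figure does not apply to the specified PET design, and glucagon versus saline has no stated power.

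This rests on the text and needs no assumption about effect size. The numbers in steps 4 and 5 of the working do: they assume a two-sided test at 0.05, paired analysis unless stated otherwise, and effect sizes chosen for illustration. The documents do not show which text is wrong.

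A secondary point does not carry the conclusion. The SAP restricts its claim to confirmed BAT-positive volunteers, whereas the protocol admits volunteers to PET on a rise in energy expenditure (Method for Objective 1) or in energy expenditure or BAT activation (Study Visits). Neither document says how BAT-positive status is confirmed.

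**What to change.** Reconcile the SAP's Statistical Analysis section with Study Visits for Objective 1, Details of PET-CT, Figure 2 and the safety section on which conditions are scanned by PET and in how many volunteers.

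**If PET is saline and glucagon:**
- Keep the cold-versus-glucagon calculation on record, marked as not applying to this design.
- For glucagon versus saline, state the power or detectable difference at the actual number scanned, with effect size, SD and paired basis.
- Analyse PET as a within-person paired difference, and keep the three-condition ANOVA for the energy expenditure and thermal outcomes of Visits 1–3.
- *Cost:* wording in both documents and one calculation; no added scan or visit.

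**If cold was a PET condition:**
- Correct the visit text and the first outcome measure.
- Say whether cold replaced saline, in which case the first outcome has no PET baseline, or was added, in which case the two-scan and 9.5 mSv statements no longer hold and must be reconciled.
- Give the effect size, SD and paired basis behind the 95%, and name a PET test that matches the conditions scanned.
- *Cost:* wording if cold replaced saline; more than wording if it was added.

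**In either case**, say how BAT-positive status is confirmed. If this does not rest on a cold PET scan, acknowledge that a null PET result is harder to separate from absence of detectable BAT, since the protocol's Background says that thermal imaging and MRI have not been validated against PET-CT.

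The downside is that the stated 95% is lost or may be replaced by a less favourable figure, and any new figure must be labelled as calculated after the original rationale.
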